If the Veteran chooses to complete the first study visit by telephone or video, Veterans will be mailed informed consent materials (VA Informed Consent form, OHSU Informed Consent form, and VA HIPAA Authorization) and first visit materials (questionnaires). After the Veteran receives the study materials, a trained study team member will call the Veteran to go through the informed consent procedures and answer any questions. If the Veteran chooses to participate, he or she will sign the VA Informed Consent form, OHSU Informed Consent form, and VA HIPAA Authorization, and mail them back to [name] using a pre-addressed and stamped envelope. Immediately after signing the consent forms, participants will have the option to complete portions of the neuropsychiatric study

visit measures, which includes the clinical interview, neuropsychiatric interview, neuropsychological assessment, and questionnaire battery via telephone or videoconference. Twelve of the fourteen neuropsychological assessments can be administered by phone or video. The remaining neuropsychological assessments will be administered at the time of the participant's next in-person visit. This research data will be collected from the participant prior to the study team receiving the signed informed consent forms and HIPAA authorization. Remaining research data and specimen collection will occur at the time of their next in-person research study visit once the signed informed consent forms and HIPAA authorization have been received.

Neuropsychiatric study visits. Clinical research staff will complete a standardized neuropsychiatric study visit protocol with eligible participants who provide informed consent. The protocol will be conducted twice for each participant (baseline and 12 weeks after DAA therapy completion).

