The protocol includes the following sources of material: 1) Breathalyzer and/or saliva alcohol test (if subject presents at study visit in an apparent intoxicated state and/or study staff have any concerns about recent alcohol use) to provide estimates of blood alcohol levels and CIWA-Ar test results to provide estimates of alcohol withdrawal symptom severity, 2) Clinical interview to collect demographic data and medical [including liver health status (e.g., fibrosis) and virological information (e.g., HCV genotype)], medication (including prior exposure to IFN-based or other antiviral therapies), and substance use history, 3) SCID-5-RV to confirm past and present substance use disorders and psychiatric diagnoses, 4) medical record review to cross-validate the psychiatric, substance use, and medical history gained through clinical interview, 5) a neuropsychological battery to measure attention, memory, and executive function, 6) a questionnaire battery to measure neuropsychiatric symptoms (e.g., depression, anxiety, fatigue and pain), 7) blood, urine, and oral fluid collection for completion of medical laboratory tests [*i.e.*, Blood is used for complete blood count (CBC), liver function panel, and HCV viral counts (obtained as part of standard care for HCV treatment). Oral fluid is used toward HIV antibody screening and alcohol testing. Urine is used for urine alcohol [*i.e.*, ethyl glucuronide (EtG) levels] and drug analysis and pregnancy tests.], 8) blood sample collection for planned experiments and for contribution to the VA Liver Disease Repository (Director: [name]), and 9) neuroimaging data [diffusion tensor imaging (DTI) and resting state and functional MRI scans are obtained at the Advanced Imaging Research Center (AIRC) at Oregon Health & Science University (OHSU) and the data are downloaded to a computer located at the VA Portland Health Care System (VAPORHCS)].

Veterans will have the option to complete portions of the neuropsychiatric study visit measures, including the clinical interview, neuropsychiatric interview, neuropsychological assessment, and questionnaire battery via telephone, videoconferencing, and/or mail. If a Veteran chooses to complete activities via telephone, video, and/or mail, a study team member will mail the Veteran the required visit materials (along with a pre-addressed and stamped envelope) and [name] or another trained, IRB-approved study team member will conduct the activities via telephone or video.

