If a Veteran chooses to complete the neuropsychological assessments via telephone or video, a study team member will administer the cognitive tests suitable for phone or video administration by reading the instructions and questions to the Veteran and recording their response. This will include twelve of the fourteen neuropsychological assessments. The remaining neuropsychological assessments will be administered at the time of the participant's next in-person visit.

Breathalyzer and saliva alcohol testing. A breathalyzer and/or saliva alcohol test is administered to participants that present at study visits in an apparent intoxicated state and/or study staff have any concerns about recent alcohol use in order to assure that participants are not impaired and to provide estimates of blood alcohol concentration (BAC) levels. The following test guidelines are used for our current and previous clinical studies in patients with AUDs. Test result = 0.00-0.05: Continue with

appointment; Test result > 0.05 but ≤ 0.08 : We are not allowed to consent a person for participation in a research study if there is any indication that their thinking may be impaired. If reasonable, given time of day and BAC level, reschedule for later in the day. If a patient is allowed to return to retest later in the day, the original BAC should be recorded on the Screen Result form. Otherwise, reschedule for a future date; Test result > 0.08 (or patient is visibly impaired): visits are discontinued and follow-up procedures are conducted, including notifying the responsible clinician ([name], Co-I). Participants that are over the legal limit will be rescheduled, and asked how they plan to get home. If taking public transportation, they will be allowed to leave unless clearly unable to take care of themselves based on clinical assessment of the responsible clinician. If driving in an automobile or motorcycle, or other personally controlled vehicle, they will be informed that they must remain at the hospital until they are no longer too inebriated to drive, will be retested using the breathalyzer or saliva alcohol test and recommended to stay in the clinic until the test is below the legal limit. If the participant threatens to leave and drive home while intoxicated, the VA Police will be called.

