Alcohol withdrawal status. The Clinical Institute Withdrawal Assessment for Alcohol, revised version (CIWA-Ar) will be administered and scored at every visit. Using this scale mild alcohol withdrawal is defined with a score less than or equal to 15. For participants who score in the mild range, we will record the score and continue with the visit. For participants in the moderate (scores of 16 to 20) or severe (scores > 20) ranges, visits are discontinued and follow-up procedures are conducted, including notifying the responsible clinician ([name], Co-I). Visits that are discontinued do to moderate or severe CIWA-Ar scores will be rescheduled.

Description of neuropsychiatric study visit measures. The neuropsychiatric study visit battery was designed to assess a full range of neuropsychiatric symptoms (e.g., AUD severity, cravings, depression, anxiety, fatigue, pain) and cognitive skills (e.g., attention, memory, executive function). The cognitive domains were selected for assessment because previous research by our group and others has demonstrated that HCV is associated with impairments in these domains (Huckans et al., 2009, Huckans et al., 2011). The present study follows up on these findings by evaluating whether individuals who receive DAA therapy for HCV evidence improved psychiatric and cognitive function, and the extent to which AUDs impact outcomes. Measures were selected because of their sound psychometric properties (e.g., reliability, validity, large normative sample that can be corrected for demographics), and because they are widely used by clinicians and have established clinical utility. *The neuropsychological measures that will be repeated have equivalent versions that will be alternated across study visits to minimize practice effects.* Measures will be administered according to published standard administration procedures.

Psychiatric and substance use disorder diagnoses

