- **SCID-5-RV.** The SCID is a copyrighted and commercially available structured clinical interview. The SCID is administered via computer or in paper-pencil form and is also available in an abbreviated format [Mini International Neuropsychiatric Interview (MINI) (Sheehan et al., 2006)]. The interviewer asks participants about whether or not they have experienced specific psychiatric symptoms across their lifetime or recently in order to determine whether they have met DSM5 criteria for psychiatric and substance use disorders. Total administration time ranges from 15-60 minutes depending on the number of symptoms an individual endorses.

Neuropsychological battery

- **Wide Range Achievement Test, Fifth Edition (WRAT5™) (Wilkinson and Robertson, 2017)** This copyrighted and commercially available assessment to measure reading, spelling, and math skills is used to estimate baseline intellectual functioning. This measure will be administered at baseline only.

- Reynolds Intellectual Screening Test (RIST) (Reynolds and Kamphaus, 2003). This copyrighted and commercially available measure is used to estimate baseline intellectual functioning. This measure will be administered at baseline only.
- Neuropsychological Assessment Battery (NAB) (Stern and White, 2003). This copyrighted and commercially available battery of subtests assesses a variety of cognitive domains. We will administer the modules on attention, memory, and executive functioning at both study visits (*i.e.*, baseline and 6-month follow-up).
 - The Attention Module includes the following subtests:
 - Digit Span – measure of auditory attention capacity and working memory
 - Dots – measure of visual attention capacity and working memory
 - Numbers & Letters – measures of sustained visual attention, speeded information processing, and inhibition/switching
 - Driving Scenes – measure of visual attention/working memory
 - The Memory Module includes the following subtests:
 - List Learning – verbal learning and memory task
 - Shape Learning – visual learning and memory task
 - Story Learning – verbal learning and memory task, involving immediate and delayed recall of verbally presented stories
 - Daily Living Memory – verbal learning and memory task, involving recall of medication instructions, and a name, address, and phone number.
 - The Executive Functions Module consists of the following subtests:
 - Mazes – measure of problem-solving and planning

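### Most of the repeated cognitive tests can switch between remote and in-person administration from baseline to follow-up, and the plan does not control, record or adjust for the switch

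*Combined protocol and SAP*

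**What the plan says.** Enrollment procedures allows remote testing: "Twelve of the fourteen neuropsychological assessments can be administered by phone or video". The other two tests wait for the next in-person visit and are not named. Informed Consent & HIPAA Authorization repeats the 12-of-14 figure for people who consent remotely.

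Neuropsychiatric study visits widens the option beyond enrollment: "Veterans will have the option to complete portions of the neuropsychiatric study visit measures", by telephone, video or mail. The same section has the visit protocol run twice, at baseline and 12 weeks after the end of DAA therapy. The remote method is described as staff administering suitable tests "by reading the instructions and questions to the Veteran and recording their response". Phone and video are not distinguished.

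Neuropsychological battery lists WRAT5 and RIST (both baseline only) and twelve NAB subtests. Four are labelled visual: Dots ("Dots – measure of visual attention capacity and working memory"), Numbers & Letters, Driving Scenes ("measure of visual attention/working memory") and Shape Learning.

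Two general safeguards appear under Description of neuropsychiatric study visit measures. One is "Measures will be administered according to published standard administration procedures". The other is that repeated tests "have equivalent versions that will be alternated across study visits to minimize practice effects". Neither mentions mode.

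In Statistical analyses and power, the outcome is each person's post-minus-pre change, analysed by general linear model with robust variance. The covariates named are age, sex, HCV genotype, changes in TLFB and CIWA-Ar, and number of provider contacts. Table 2, note c, gives the cognitive outcomes as NAB module index change scores.

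**The concern.** A change score removes a person's stable level only if both measurements are made in the same way. If someone takes Attention subtests by phone at baseline and in the clinic at follow-up, any difference between the two modes becomes part of that person's change and cannot be told apart from an effect of viral clearance or alcohol use.

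There are three possible consequences:

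- If switching is equally common and similarly directed in all four groups, the between-group contrasts lose precision but are not biased.
- If it differs by group, the AUD, HCV or interaction contrast is biased.
- If it runs mainly one way, the within-group improvement in Hypothesis 1.1 is biased, even when groups switch alike.

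The plan already takes between-visit comparability seriously: it alternates test forms, and it adjusts for provider contacts because these may differ by HCV status. Mode could differ for related reasons, since the notes to Table 1 say about half of those starting DAA therapy are followed by phone. That is a plausible route, not a documented imbalance.

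**Working it through.** **1. Counting tests (Neuropsychological battery).**

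- Battery: WRAT5 + RIST + 4 Attention + 4 Memory + 4 Executive = 14, which matches the stated total.
- Repeated tests: 14 − 2 baseline-only = 12, all NAB subtests.
- In-person-only tests: 14 − 12 = 2. Even if both are NAB subtests, 12 − 2 = 10 repeated subtests can change mode. If they are WRAT5 and RIST, all 12 can.
- Visual subtests classed as remote: at least 4 − 2 = 2.
- Three of these four are in the Attention module, so at least 3 − 2 = 1 visual Attention subtest is classed as remote.

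**2. Reproducing Table 2.** Inputs: 30 per group, two-sided alpha 0.05 for main effects and 0.10 for the interaction. For Attention, SD(diff) is 2.25, the main effect 1.25 and the interaction 2.1.

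- Main effect: SE = 2.25 × √(2/60) = 0.411; 1.25/0.411 = 3.04. Noncentral t (116 df) gives power 0.855, against 0.85 stated.
- Interaction: SE = 2.25 × √(4/30) = 0.822; 2.1/0.822 = 2.56. Power is 0.815, against 0.81 stated.
- Main effects for the other modules: Memory 0.903 (stated 0.91) and Executive function 0.775 (stated 0.78).

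The table reproduces, and its inputs contain no allowance for mode variation.

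Steps 3 to 5 rest on assumptions, because the documents give no mode effect and no switching rates. Let m be the shift in the module score caused by switching, in units of SD(diff), and p the share who switch, all in one direction.

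**3. Equal switching in all groups (lost precision).** SD becomes SD(diff) × √(1 + m²p(1 − p)).

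- Mild case, m = 0.5, p = 0.10: 2.25 × √1.0225 = 2.28.
- Strong case, m = 1.0, p = 0.50: 2.25 × √1.25 = 2.52.

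| Module | Main-effect power, no switching | Mild | Strong |
|---|---|---|---|
| Attention | 0.855 | 0.847 | 0.770 |
| Memory | 0.903 | 0.897 | 0.830 |
| Executive function | 0.775 | 0.766 | 0.681 |

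Attention interaction power falls from 0.815 to 0.807 (mild) or 0.735 (strong).

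**4. Switching that differs by HCV status (bias).** Bias = m × SD(diff) × Δp, where Δp is the difference in the share switching. Take m = 0.5 and 10% switching in the lower group.

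- Δp = 0.10: 0.5 × 2.25 × 0.10 = 0.11 points; 0.11/1.25 = 9% of the target effect.
- Δp = 0.40: 0.5 × 2.25 × 0.40 = 0.45 points; 0.45/1.25 = 36%.

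With no true HCV effect, and SE (in SD(diff) units) = √{[1 + m²p₁(1 − p₁)]/60 + [1 + m²p₀(1 − p₀)]/60}, the nominal 0.05 test rejects with probability 0.058 at Δp = 0.10 and 0.186 at Δp = 0.40.

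**5. One-directional drift within a group (Hypothesis 1.1).** Bias in the mean change = m × SD(diff) × net share switching, meaning the share moving one way minus the share moving the other. With m = 0.5 and a net share of 10% to 40%, this is again 0.11 to 0.45 Attention points. The Table 2 change for the AUD-/HCV+ group is 3.7 points, so the bias is 3% to 12% of it (0.11/3.7 and 0.45/3.7).

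**The case against.** The plan has more protection than the 12-of-14 figure suggests. Remote testing is confined to tests judged suitable, video can display stimuli, visit materials are mailed, a licensed neuropsychologist trains and supervises test administration, and the investigator checks procedures at least monthly. A reader might infer that some of the twelve cannot be given remotely at all. The documents do not support that: a visual label does not rule out video or mailed stimuli, and Mazes is described as problem-solving and planning. What remains is that the two in-person tests are unnamed, phone and video are treated alike, and reading aloud does not explain how a visual subtest is given.

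A reader might also infer a contradiction with the commitment to published procedures. That sentence does not say administration must be in person, and what the publishers allow depends on manuals outside these documents.

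The covariate list is open: variables that may change over time are introduced by examples. Mode is therefore unnamed rather than excluded. This is fair, but a covariate can be used only if it is recorded, and no text provides for that. Robust variance does not help, because it leaves a shift in the mean untouched.

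Finally, no passage indicates that switching differs by group. Switches in opposite directions offset each other, and subtests kept in person dilute any effect on the module score. All of this stands, and it limits the claim to a risk.

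**Conclusion.** The gap is real. At least 10 of the 12 subtests behind the three cognitive change scores can change mode between visits, and nothing in the plan controls, records or adjusts for it. That much follows from the documents by counting.

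It does not follow that the cognitive contrasts are biased, though a reader might infer it. Bias needs a mode effect together with either unequal switching between groups or a net drift in one direction, and the documents report none of these. The bias and power figures show only how much mode could matter. They assume a shift of 0.5 SD(diff) (up to 1.0 in the power calculation), switching all in one direction, and switching shares chosen for illustration. On those terms the result ranges from a negligible loss of power to a bias of about a third of the Attention target. The point deserves action because the exposure is avoidable at low cost.

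**What to change.** 1. Name the two in-person-only tests, and say how phone and video administration differ.
2. Give the four NAB subtests labelled visual, and Mazes if it needs a visual stimulus, at the in-person visits already required for specimens at both time points.
3. For the remaining subtests, make each participant's baseline mode the default at follow-up. A default is better than an absolute rule, which would force remote retesting of someone already on site or lose the score.
4. Record mode (phone, video, in person) for every subtest at every visit.
5. Add a signed mode-change covariate to each cognitive model, for example the number of the module's subtests that moved from remote to in person minus the number that moved the other way. Add a sensitivity analysis restricted to same-mode pairs, and tabulate switching by group.

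The cost is less flexibility for remote visits, somewhat longer in-person visits and one extra model term. No new visit is needed. The covariate removes only an average shift, and the same-mode subset is smaller and self-selected, so the two should be read together. The cover page is dated October 2024 and concerns summary results. If testing has finished, only the analysis steps remain open, wherever mode can be recovered from visit records.

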Monetary Incentive Delay Task (MID): The MID is a validated task to examine incentive-reward reactivity of the ventral striatum. The task requires little cognitive demand and participants simply respond to a brief presentation of a visual target to win or lose money. Participants will not receive the winnings from this task. The MID task session consists of 180 6-second trials. During each trial, participants are shown a cue (cue phase, 1 second), indicating that they have the potential to win or lose money (\$0.20, \$1 or \$5) or that no money is at stake for that trial (Control). A fixation cross is present during a variable interval (anticipatory delay phase, 2000–2500 ms), and when a target appears, participants press a button (target phase, 160–260 ms). For WIN trials, participants will be told that if they successfully press the button while the target is onscreen (a "hit") they will win the amount of money indicated by the cue. For LOSE trials, participants will be told that no money will be won or lost for hits, but misses will lead to a loss of the amount indicated by the cue for that trial. By contrasting brain activations in the anticipatory delay phase in WIN trials vs. Control trials it is possible to examine the extent to which the anticipation of potential reward modulates ventral striatal activity during this preparatory period. A Feedback phase (1650 ms) follows the target's disappearance. Feedback will display amount won or lost for each trial and total cumulative winnings.

**Methodological details for imaging acquisition, processing, and analysis were provided by the [name] lab and are summarized on pages 10-11.*

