MRI Imaging Acquisition: We will use the Human Connectome Project (HCP) Lifespan Protocol using a 3T Siemens Magnetom Prisma scanner and a 32-channel phased array head coil. **fMRI (T₂^{*}-weighted):** Three (2 PDD and 1 DSNBACK) T₂^{*}- weighted echo-planar imaging (EPI) functional runs will be acquired (60 slices, 2 mm thick, TR/TE/α=2000 ms/38 ms/55°, matrix=128 × 128, FOV=220 mm², PAT mode/Accel factor = GRAPPA/2, 310 volumes per run) with an in-plane pixel size of 2.0 mm² while subjects perform the PDD or the DSNBACK. Each run will be 10.3 minutes long. **rsfMRI:** Identical to fMRI settings with 200 volumes. **High-resolution anatomical (T₁-weighted [T_{1w}]):** One magnetically prepared rapid acquisition gradient echo (MPRAGE) (208 0.8 mm isovoxels, TR/TE/TI/α = 2400 ms/2.24 ms/1060 ms/8°, FOV=256x240 mm, 2x Parallel Imaging, duration 6.38 min), will be acquired for co-registration with functional images and statistical overlay. **High-resolution anatomical (T₂-weighted [T_{2w}]):** 208 slices, 0.8 mm isovoxels, TR/TE: 3200 ms/564 ms; variable flip angle; FOV 256x263 mm, 2x Parallel imaging; Futsyion 5.57 min. **HARDI:** Two HARDI scans will be acquired (66 axial slices, 2.2 mm thick, TR/TE/α = 4300 ms/96 ms/90°, FOV= 25.6 cm², PAT mode /Accel factor = GRAPPA/2) consisting of six non-diffusion weighted (B₀) images followed by 32 non-collinear directions at B₀ = 1000 s mm⁻² and at B₀ = 2000 s mm⁻². Each HARDI scan lasts 4.73 min.

fMRI Standard Preprocessing: Task-related and resting-state fMRI data will be preprocessed identically. We include only scans with minimal movement (< 3 mm) and free of artifacts (Murphy et al., 2013). Functional images will be realigned for motion corrections, unwarped then co-registered to structural images for each subject and then transformed to Talairach coordinates and then resampled into atlas space with 3 mm isovoxels. Motion correction is applied with the standard 6 parameters and then frame-by frame spatial deviations are assessed with the temporal derivative of the time course.

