The anatomical volume is then segmented into gray matter, white matter, and cerebrospinal fluid. Next, we apply a temporal bandpass filter ($0.009 \text{ Hz} < \nu < 0.08 \text{ Hz}$), spatial smoothing (6 mm full width at half maximum (FWHM) Gaussian kernel), regression with the 6 rigid body motion parameters, regression of the whole brain signal and regression of the signal for ventricles and white matter. Opposite phase-encode polarity spin echo images will be used to estimate the B_0 distortion field, which will be applied to each gradient echo frame after accounting for estimated head motion. Gradient nonlinearity distortions will be corrected using scanner-specific field maps. Both corrections are vital for proper registration to structural images. Images will be preprocessed using AFNI_16.1.26. To enable cortical surface-based analyses, fMRI time courses will be sampled to the cortical surface mesh, using the extent of overlap with the cortical ribbon as a weighting factor to account for partial voluming. Voxels with high variability relative to their local neighborhood will be excluded. The functional EPI images will be despiked (3dDespike), slice time corrected (3dTshift), motion corrected (3dvolreg), aligned to warped MPRAGE (align_epi_anat.py) and corrected for oblique slice acquisition. A 4 mm FWHM three-dimensional Gaussian blur will be applied to the functional images (3dmerge) and each voxel time series will be scaled to have a mean of 100 (3dTstat, 3dcalc).

Anatomical (T_{1w} and T_{2w}). MPRAGE and T_{2w} structural images will be corrected for gradient nonlinearity distortions using scanner specific, nonlinear transformations, provided by MRI scanner manufacturers, and verified using phantom scans. Spatial distortion in the readout direction due to B_0 variation will be corrected based on the distortion maps generated from our fast field mapping. T_{2w} images will be registered to T_{1w} images using mutual information after coarse pre-alignment via within-modality registration to atlas brains. Intensity non-uniformity correction will be performed by dividing image intensities by a smooth bias field estimated from the geometric mean of the T_{1w} and T_{2w} images. Anatomical scans will be corrected for oblique acquisition, skull stripped (3dSkullStrip), and warped into MNI-152 space with @auto_tlrc.

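### As written, task fMRI receives the resting-state band-pass and whole-brain signal regression, and a second list of functional steps is left unreconciled; for the one named task contrast the band-pass alone removes about 20% of regressor variance under stated assumptions

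*Combined protocol and SAP*

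**What the plan says.** All places are in the combined protocol and SAP, Research Design and Methods.

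- **fMRI Standard Preprocessing, the rule.** "Task-related and resting-state fMRI data will be preprocessed identically".
- **Same section, first list.** "Next, we apply a temporal bandpass filter" (0.009 to 0.08 Hz), then 6 mm smoothing, motion regression, and "regression of the whole brain signal and regression of the signal for ventricles and white matter". Functional images go to Talairach space.
- **Same section, second list.** AFNI despiking, slice timing, motion correction and alignment to the warped anatomical image. Then "A 4 mm FWHM three-dimensional Gaussian blur will be applied to the functional images", and each voxel series is scaled to a mean of 100. This list names no band-pass and no whole-brain regression. The anatomical text warps to MNI-152.
- **Monetary Incentive Delay Task (MID).** 180 trials of 6 s, with an anticipation phase of 2.0-2.5 s after a 1 s cue. The contrast is introduced with "By contrasting brain activations in the anticipatory delay phase in WIN trials vs. Control trials".
- **Balloon Analogue Risk Task (BART).** Event-related, in two 10-minute runs. The outcome variables listed are behavioural: pumps, cash-outs, earnings and reaction times.
- **MRI Imaging Acquisition.** TR 2 s, "310 volumes per run", acquired "while subjects perform the PDD or the DSNBACK". "Each run will be 10.3 minutes long".
- **Neuroimaging measures (statistical section).** Covers resting-state connectivity and discounting tasks. It gives no first-level model for BART or MID.

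**The concern.** A low-pass at 0.08 Hz and whole-brain regression are connectivity steps. Event-related responses carry power above 0.08 Hz, and any task-locked component of the global signal is regressed out with it. MID trials recur every 6 s (0.167 Hz), about twice the upper cut-off.

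Two things are at stake. First, the task contrast loses signal. Depending on a task model that is not stated, this appears either as a shrunken estimate or as a larger standard error. Residual degrees of freedom are also overstated if the filter is ignored. Second, two analysts could follow this section and produce different data: 6 mm, 4 mm or both; filtered or not; Talairach or MNI-152. Cortical activity is part of the primary objective, so the task stream should be fixed before the contrasts are run.

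**Working it through.** The plan states no signal-loss figure, so there is none to reproduce. One internal check agrees: 310 volumes × 2 s = 620 s = 10.33 min, against the stated 10.3 min.

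**Inputs from the documents.** Pass band 0.009-0.08 Hz; 180 MID trials of 6 s; 1 s cue, then 2.0-2.5 s anticipation.

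**Assumptions.** TR 2 s for MID (the document gives it for PDD/DSNBACK runs); trial mix 40% WIN, 40% LOSE, 20% Control in random order; double-gamma haemodynamic response.

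**Step 1: share of the spectrum kept.** Nyquist frequency = 1/(2 × 2 s) = 0.25 Hz. Kept: (0.08 − 0.009)/0.25 = 0.071/0.25 = 28%.

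**Step 2: regressor variance removed, MID WIN minus Control.** Build the anticipation-phase regressor, convolve it with the response, sample every 2 s, and take the share of variance outside the band, averaged over random trial orders.

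| Part of spectrum | Share of regressor variance |
|---|---|
| Below 0.009 Hz | about 10.0% |
| Above 0.08 Hz | about 10.6% |
| Total removed | about 20.6% |

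Across response shapes, MID WIN-based regressors lose about 18-25% (double-gamma settings) or 32-36% (single-gamma). Against an ordinary high-pass at an assumed 1/128 Hz, the extra loss is about 11-18% and 25-30% respectively.

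**Step 3: effect on the estimate.** Let k be the retained share, here 1 − 0.206 = 0.794.

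- Data filtered, design not: expected coefficient = k × true value, about 0.80.
- Data and design both filtered: unbiased, with white-noise SE multiplied by 1/√k = 1/√0.794 = 1.12.
- In either case contrast-to-noise falls to √k = √0.794 = 0.89 of the unfiltered value.

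**Step 4: what dropping the low-pass recovers.** If drift terms still take the 10.0% below 0.009 Hz, the retained share rises from 0.794 to 0.900. First-level contrast-to-noise improves by √(0.900/0.794) = 1.06.

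**Step 5: degrees of freedom.** An 18-minute MID session (180 × 6 s = 1,080 s) at TR 2 s gives 540 volumes. The filter leaves about 0.284 × 540 = 153 independent components before model terms are subtracted.

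**Step 6: what cannot be fixed from the documents.**

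- *Whole-brain regression.* If the task regressor correlates r with the global signal, about r² is removed. An assumed r of 0.1 to 0.5 gives 1% to 25%.
- *BART imaging.* No contrast is named. Assumed pump, cash-out, explosion and active-minus-control regressors lose about 12-44%, depending on response shape and pump interval.

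**Step 7: smoothing.** If both blurs are applied, the combined kernel is √(6² + 4²) = √52 = 7.2 mm.

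**Step 8: acquisition text.** The runs described last 10.3 min and name PDD and DSNBACK. An 18-minute MID session does not fit one such run, so this text has not been adapted to the current tasks.

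**The case against.** The second list could be the intended task stream, since it names neither the band-pass nor whole-brain regression. That is possible, but the sentence on identical handling contradicts it and nothing else assigns the list to task data. Double smoothing is likewise only one reading.

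The size is also open to challenge, and most of that challenge stands. About half of the 20% lies below 0.009 Hz, where ordinary drift terms would remove much of it anyway. Variance removed is not power lost: contrast-to-noise falls to 0.89, and between-subject variance dilutes this further in group tests. The filter is the same for all groups and visits.

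Three stronger readings are tempting and are not supported:

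- *That the band-pass and whole-brain regression together remove 20-37%.* Losses of this order come from the band-pass alone, under assumed timing and response shapes. The whole-brain share is unknown.
- *That the impulsivity hypotheses (1.2 and 2.2) rest on these contrasts.* The BART section lists behavioural variables, which preprocessing does not touch. The statistical section takes impulsivity from discounting curves. Much of 1.2 and 2.2 concerns FA and MD.
- *That the task estimates will be biased.* This depends on whether the design is filtered too, which the plan does not say.

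**Conclusion.** The point holds as a specification defect with a moderate analytic cost. The text applies the resting-state stream to task data and leaves two step lists, two kernels and two template spaces unreconciled; none of that depends on simulation.

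The size does depend on assumptions. For MID WIN against Control the band-pass removes about 20% of regressor variance (18-36% across response shapes), of which about half of the 20% is recoverable. The consequence is either a contrast of about 0.80 of its value or a first-level SE about 1.12 times larger, and degrees of freedom must reflect the filter under both. These figures rest on the assumed TR, trial mix and response. BART imaging losses and the whole-brain regression loss remain undetermined. The point should be addressed before the task data are analysed, but it does not threaten the behavioural, diffusion or laboratory outcomes.

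**What to change.** Replace the sentence on identical preprocessing with two named streams.

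- **Rest:** band-pass, nuisance and whole-brain regression, 6 mm smoothing.
- **Task (BART, MID):** the listed AFNI steps with one 4 mm blur and scaling; drift and motion terms inside a stated first-level model; no 0.08 Hz low-pass. Leave whole-brain regression out of the primary task model.

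In the first-level model, name the regressors and the contrasts, including any BART imaging contrast. If any filter is kept, state that it is applied to data and design alike and that degrees of freedom are adjusted. State one template space. Update the acquisition text from PDD/DSNBACK runs of 10.3 min to the BART and MID runs actually acquired, with their TR and volume counts.

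The cost is wording plus some reprocessing; no new data are needed. The downside is that slightly more high-frequency noise stays in the task data.
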